For the second primary objective, previous literature suggests that the average difference in % change LV dP/dt max between MultiSpot SEQ and BiV pacing is 3% (^{6, 17}) in a normal HF population. Assuming an increased difference between MultiSpot SEQ pacing and BiV pacing within the targeted study population similar to the increase for the difference between MultiSpot SYN pacing, i.e., 1 %, the expected difference between MultiSpot SEQ pacing and BiV pacing is 4%. Assuming this difference and a standard deviation of 7%, a sample size of 34 patients has 90 % power to demonstrate superiority.

For the secondary objective 1, a power of 80% is achieved with 34 patients. Based on previous research (iSPOT study, ¹⁹), we assume that the lower-border of the 95 % confidence interval for % change MultiSpot SYN to baseline (AAI mode) in the targeted patient population is 12.6. In this study we consider MultiSpot SEQ non-inferior to MultiSpot SYN if the difference in their means is less than a quarter of the difference between MultiSpot SYN pacing and baseline. The non-inferiority margin is thus chosen to be – 3%. Assuming the expected difference in percentage change dP/dt max between MultiSpot SEQ and MultiSpot SYN pacing is 0.5% and a standard deviation in differences of 7%, 34 patients would have 80% power to demonstrate non-inferiority of MultiSpot SEQ to MultiSpot SYN.

C.8 Number of investigation sites and study duration

The study is expected to be conducted in approximately 10 centers in Europe. At the time this Clinical Investigation Plan was finalized, not all participating investigation sites were identified. A list of participating investigation sites and investigators will be available under a separate cover. The study will enroll up to 40 subjects who fulfill the eligibility criteria and who have completed the EP study procedure. It is anticipated that this study will require approximately 12 to 18 months for subject enrollment. Patients' participation in this study is expected to last approximately between 1 day and 3 months, depending on the time between enrollment and the EP study and the duration of hospital stay after this research study, or EP related procedure, or the CRT-implant. Subjects must meet all of the inclusion criteria and none of the exclusion criteria to be included in the study.

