Figure 5: Description of the pacing protocol. Part A is depicting the MultiSpot-SYN protocol while Part B is depicting the MultiSpot-SEQ protocol. Both protocols require the determination of the patient-specific AV-delay while Part B also requires the determination of patient-specific VV-delays. Part C is displaying the pacing procedure for 1 out of 5 total AV delays during which the positive dP/dt_{max} will be measured. Each pacing ON and OFF setting will last 10-15 sec. The repetition of steps is used to increase sensitivity of the positive dP/dt_{max} measurements. Five AV delays will be assessed: optimal AV, optimal AV delay +/- 30 and +/- 60 ms.

F.3 Data collection requirements

Clinical data will be collected at enrollment, baseline and during the study procedure. Table 2 summarizes the data requirements. Patients' participation in this study is expected to last approximately between 1 day and 3 months, depending on the time between enrollment/baseline and the EP study and the duration of hospital stay after the research study, or EP related procedure or the CRT-implant. The EP study visit should take place within 3 months after the MRI has been obtained. In case the EP study visit is not done within 3 months after the MRI, the patient should be exited from the study.

Subjects, who complete all study procedures, will be exited from the study just before the moment of hospital discharge. This will be documented on the Study Exit eCRF. There will be no further follow-up required for subjects that are exited from the study since no investigational products will be implanted or used in the study.

Table 2: Data Collection Requirements

Data	Baseline	EP Visit
Inclusion/Exclusion Criteria	x	
Subject Informed Consent	x	
Demographics	x	
Physical examination	x	
LVEF Within 3 months prior to enrollment, otherwise a new measurement should be performed	x	
Surface ECG Within 3 months prior to enrollment, otherwise a new ECG should be performed	x	x
Echocardiogram If available within last 3 months, otherwise not collected	x	
NYHA Class	x	
Medical history	x	
Cardiovascular medications	x	
MRI (structural and functional)	x	
Non-invasive blood pressure	x	x
Venogram		x
Invasive blood pressure		x
LV pressure		x
LV lead implant location (Chest X-ray)		x
Unipolar and Bipolar electrograms		x
Adverse events	x	x
Device deficiency		x
Deviation	x	x
Exit	x ¹	x

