¹ In case the MRI is done solely for the study: If the patient has ischemic etiology and a LBBB conduction pattern and QRS-width above 150ms, the MRI images should be analyzed immediately to detect scar. If scar is not present on late gadolinium enhanced MRI, the patient should be exited from the study prior to EP visit

F.4 Role of the sponsor’s representatives

Sponsor’s representatives (e.g. Field Clinical Engineer, Field CRS, Technical Consultant) may provide support as required for the clinical study, including technical support during implant/procedure including completion of a technical support sheet and/or technical support. Documentation of study training and qualification of sponsor representatives will be maintained by Medtronic. The sponsor’s representatives providing technical support may be listed on the sponsor technical support list.

F.5 Source documents

Source documents may be the PIC, hospital/clinic files, Electronic Media (MRI images, Echo images), programmer or ECG printouts, worksheets, MRI images and eCRFs.

The investigator will clearly mark the clinical records to indicate that the subject is enrolled in this clinical study.

Data that could be recorded directly on the eCRF and considered as source data are listed in section G.1.2.

F.6 Adverse events and Device Deficiencies

F.6.1 Definition/classification

Timely, accurate, and complete reporting and analysis of safety information for clinical studies are crucial for the protection of subjects, investigators, and the sponsor. Reporting and analysis of safety data are mandated by regulatory authorities worldwide. All events and deaths for the SYNSEQ study will be collected, classified, reviewed and reported from enrollment up till study exit. Documented pre-existing conditions are not considered AEs unless the nature or severity of the condition has worsened.

For the purposes of the clinical report, Medtronic will classify each Adverse Event according to ISO 14155:2011.

Where the definition indicates “device”, it refers to any device used in the study. This might be the device under investigation, or any market released component of the system.

Adverse Event (AE): (ISO14155:2011 3.2)

Any untoward medical occurrence, unintended disease or injury, or untoward clinical signs (including abnormal laboratory findings) in subjects, users or other persons, whether or not related to the investigational medical device

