An adverse event inherent to a surgical procedure that is expected to occur in all subjects for a projected duration according to the Investigator's opinion, including, but not limited to:

Event Description	Time Frame (Hours) from the Surgical Procedure
Anesthesia related nausea / vomiting	24
Low-grade fever (<100°F or 37.8°C)	48
Pocket site / Incisional pain	72
Mild to moderate bruising / ecchymosis	168
Sleep problems (insomnia)	72
Back pain related to laying on table	72
Shoulder pain/discomfort/stiffness related to shoulder immobilization during procedure	72

Further adverse event definitions:

Relatedness	
Procedure Related	An adverse event that occurs due to any procedure related to the investigational study procedure/protocol
System Related	
 • Pacing system Related: An adverse event that results from the presence or performance (intended or otherwise) of the Pacing system (Connection Box, hand-held pacers and connection cables) • Lead Related: An adverse event that results from the presence or performance (intended or otherwise) of the right atrial, right ventricular or left ventricular lead • Implant or Introduction Tool Related: An adverse event that results from the presence or performance (intended or otherwise) of the implant or introduction tool • LV Catheter Related: An adverse event that results from the presence or performance (intended or otherwise) of the LV Catheter
Timing	

Pre-study procedure testing AE	An adverse event that occurs after the patient informed consent form has been signed but before the skin incision related to the investigational study procedure/protocol
During study procedure testing AE	An adverse event that occurs during investigational study procedure testing/protocol
Post study procedure testing AE	An adverse event that occurs between the completion of skin closure for the investigational study procedure testing/protocol and before hospital discharge of the patient
Other	
Hospitalization	A therapeutic inpatient hospitalization (excludes outpatient and emergency room visits) lasting greater than or equal to 24 hours.

F.6.2 Recording and reporting of Adverse Events

Adverse Event (AE) information will be collected throughout the study and reported to Medtronic on an Adverse Event Form, one for each Adverse Event. This Adverse Event form must be entered in the database.

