A subject will be exited from the study in the event that he or she is unable to participate, expresses a desire to withdraw, or is unwilling to continue participation in the study. The reason for withdrawal needs to be documented in the subject's hospital record and in the eCRF. The subject should be informed that their future care or treatment will not be affected in any way as a result of choosing to not participate in this study. Furthermore,

alternative treatments and medical consequences of exiting the study should be discussed with the subject. Any significant new findings related to the study that may develop, which may relate to the subject's willingness to continue participation, should be communicated to the subject. Unless the patient explicitly revokes informed consent, available data will be reported.

A subject may be exited from the study if an investigator feels it is necessary to withdraw the subject from the study due to a medical condition or other reason. In such cases, the subject will be notified and provided an explanation regarding the reasons for the study exit. Unless the patient explicitly revokes informed consent, available data will be reported.

Upon withdrawal from the study, no further study data will be collected for the subject.

If discontinuation is because of safety or lack of effectiveness, the subject shall be asked to be followed for collecting safety data outside the clinical study.

The subjects who withdraw or who are withdrawn are not replaced.

If the subject is determined to be lost to follow-up, the details regarding a minimum of two attempts and the method of attempt (e.g., one letter and one phone record or two letters) to contact the subject must be documented in the patient medical record. Any additional regulations set forth by the governing MEC must be followed.

F.8 Study deviations and CIP changes

A study deviation is an event where the investigator or site personnel did not conduct the clinical study according to the Clinical Investigational Plan or Clinical Investigation Agreement. The investigator is not allowed to deviate from the above mentioned documents except with prior approval and under emergency circumstances. All deviations shall be documented and explained, regardless the reason for the deviation.

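### Safety collection stops early for a patient withdrawn during or after the EP procedure, while completers are covered to discharge, and other sections of the protocol contradict that stop

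*Protocol*

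**What the plan says.** Protocol F.7 governs withdrawal, whether by the patient or by the investigator for a medical condition or another reason. It states: "Upon withdrawal from the study, no further study data will be collected for the subject". Where the reason is safety or lack of effectiveness, "the subject shall be asked to be followed for collecting safety data outside the clinical study". F.7 also protects what has already been recorded: "Unless the patient explicitly revokes informed consent, available data will be reported".

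F.6.1 sets the safety window for everyone: "All events and deaths for the SYNSEQ study will be collected, classified, reviewed and reported from enrollment up till study exit". For completers, F.3 fixes the end of that window: "Subjects, who complete all study procedures, will be exited from the study just before the moment of hospital discharge". The timing definitions in F.6.1 match this; a post-procedure event is "An adverse event that occurs between the completion of skin closure for the investigational study procedure testing/protocol and before hospital discharge of the patient".

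Two other places impose reporting duties with no stated cut-off at withdrawal. Table 3 requires the investigator to pass on new information about an SAE or SADE already reported. F.6.7 requires every subject death to be reported and gives the AEAC the final adjudication.

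Protocol H.1 and SAP 7.1.3 report safety on all patients who signed consent. SAP 7.10 tabulates the number of events and the number and percentage of patients with one or more events, by seriousness, relatedness and preferred term, with deaths by classification. It has no rule for data gathered outside the study.

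**The concern.** A complication during the procedure can be the reason a patient is withdrawn. If F.7 and F.6.1 are followed literally, the safety window then closes because of the safety outcome, while the patient remains in the denominator. SAP 7.10 uses plain counts and percentages with no adjustment for time observed, so any loss can only lower the numerators.

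Section J.2 expects no lower risk than routine care: it describes study risk as somewhat higher than that of standard CRT implantation. Some of the risks it lists, such as infection, hematoma and kidney dysfunction, can appear after the procedure itself. The hours or days before discharge are therefore a period in which a complete record matters, and the AEAC can review only what is reported to it.

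**Working it through.** No sample size, power or event figure in the plan bears on this point, so there is nothing to reproduce. The check is a comparison of passages, followed by an illustration of scale.

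**Step 1. Compare the windows after the procedure has started.**

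| Patient | Window closes | Source |
|---|---|---|
| Completer | Just before discharge | F.3, F.6.1 |
| Withdrawn during or after the procedure | At withdrawal | F.7, F.6.1 |

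The difference is the time from withdrawal to discharge. It does not extend further, because completers have no follow-up after discharge either. A patient withdrawn before the EP visit may lose a longer period, since participation "is expected to last approximately between 1 day and 3 months", but that patient has not undergone the study procedure.

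**Step 2. Ask which rows of the SAP 7.10 tables can change for a patient withdrawn because of an adverse event.**

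- Patients with one or more events: no change, because the triggering event is recorded before exit and kept.
- Number of events: can be too low.
- Individual preferred terms: a new term arising after withdrawal can be absent.
- Seriousness: an event recorded as non-serious that worsens before discharge can stay non-serious. The new-information wording in Table 3 is attached to SAEs and SADEs among the event classes, not to the rows for ADEs or other AEs.
- Updates to an SAE or SADE already reported: required by Table 3, stopped by F.7.
- Deaths: required by F.6.7, but collected only to exit under F.6.1.

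For the last two rows the protocol gives two answers. What is captured depends on which section the site follows.

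**Step 3. Illustrate the scale.** Take N = 40, the planned number of eligible subjects completing the EP procedure. The number of patients affected is not in the documents; 0 to 4 is an assumption for illustration. Exact (Clopper-Pearson) 95% limits are used. For 0/N the upper limit is 1 − 0.025^(1/N), so 1 − 0.025^(1/40) = 8.8%.

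| Patients with the event | Percentage | Exact 95% CI |
|---|---|---|
| 0/40 | 0% | 0 to 8.8% |
| 1/40 | 2.5% | 0.06 to 13.2% |
| 2/40 | 5.0% | 0.6 to 16.9% |
| 3/40 | 7.5% | 1.6 to 20.4% |
| 4/40 | 10.0% | 2.8 to 23.7% |

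Each patient missed in a given row moves it by 1/40 = 2.5 percentage points. The safety denominator is everyone who consented, which can exceed 40 because some patients may be exited after the MRI. The step is then smaller: at an assumed 50 consented, 1/50 = 2.0 points.

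**The case against.** The strongest reply is that the protocol already covers the worst cases. F.6.7 asks for all subject deaths without excepting withdrawn patients, and F.6.5 has the AEAC review all deaths. Table 3 asks for new information on reported SAEs and SADEs, so a deterioration that is the course of a reported serious complication would be sent in. This stands in part. A reader might infer from F.7 that a later in-hospital death or worsening is certain to be left out of AEAC review and the SAP tables; the documents do not support that. They support a conflict, which leaves capture uncertain.

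A second reply is that stopping the EP procedure for a complication is not the same as leaving the study. The Synopsis and SAP 7.1.1 have subjects exit just before discharge without limiting this to completers, F.7 says only that the investigator may exit a patient, and SAP 7.4 treats configurations that could not be applied as missing data. This is fair, and it means early exit may be uncommon. But F.7 does not separate the two, and it also says that a subject unable to participate will be exited.

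Third, a reader might infer that the tables lose the patients who did worst. They do not: these patients, their triggering event and all earlier data stay in the All Enrolled tables.

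Fourth, SAP 7.10 refers to a separate Safety Plan that is not among the documents reviewed and might close the gap. That cannot be excluded, but the protocol would still say the opposite.

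**Conclusion.** The point holds in a limited form. As written, F.7 and F.6.1 end safety collection early for a patient withdrawn during or after the EP procedure, relative to completers, and the patient stays in the denominator. New events, preferred terms, event counts and changes to serious in the rest of the hospital stay can be missed. Deaths and updates to reported SAEs or SADEs may be missed, because F.7 and F.6.1 cannot be reconciled with F.6.7 and Table 3.

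The direction of any error is downward. Its size cannot be estimated, since the documents give neither a withdrawal rate nor a rate of events after withdrawal; the 2.5-point step is an illustration that assumes one missed patient and a denominator of 40. A claim that the reported rates are biased by a known amount would go beyond the text.

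The conclusion assumes that sites follow F.7 literally and that the Safety Plan does not override it. The efficacy objectives are not affected. The change is still worth making, because the loss would be triggered by the outcome being measured and the remedy is cheap.

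**What to change.** 1. In Protocol F.7 and F.6.1, state that once the EP procedure has started, adverse events and deaths are collected as study data until hospital discharge, whether or not the patient is withdrawn, unless the patient revokes consent. This replaces follow-up outside the study for that period.
2. Reconcile F.7 and F.6.1 with Table 3 and F.6.7, so that one rule covers new information on reported events and deaths after withdrawal.
3. In SAP 7.10, state that these events belong to the Safety set and go to the AEAC.

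Discharge is the right end point for the comparison because it is the one completers have. Collecting until each triggering event resolves could run past discharge and would create the opposite imbalance.

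The cost is wording in the protocol, SAP and consent form, and a few extra CRF pages for patients who are mostly still in hospital. Sample size and the efficacy analyses do not change.

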- Investigator's Brochure and Instructions for Use
- Medtronic and EC approved Patient Informed Consent

- Competent authority approval or notification, if required
- EC approval documents and documentation that the investigator did not participate in the approval process
- Fully signed clinical investigation agreement and confidentiality agreement (if not included in the clinical investigation agreement)
- Financial disclosures, if local requirements
- Insurance certificates
- Completed Delegated Task List and Curriculum Vitae of all investigation site personnel
- Training documentation of all investigation site personnel
- Relevant communications
- Subject screening log and/or subject identification log
- Signed, dated and fully executed informed consent forms
- Fully executed eCRFs and corrections
- Reports of Adverse Events and Device Deficiencies
- Connection box disposition log containing serial numbers of connection boxes brought to the site by Medtronic personnel for the EP study visit, received dates of the connection boxes, subject IDs of the subjects paced with the connection box and dates the connection boxes are taken back to Medtronic after the EP study visit.
- Final report
- Any other records that local regulatory agencies require to be maintained

1.3.2 Investigator reporting responsibilities

Each investigator must submit the final report to their EC (each investigator for their own EC). The final report contains a summary of the clinical study's findings and conclusions.

The investigator is responsible for the preparation (review and signature) and submission to Medtronic of all case report forms. If any action is taken by an EC with respect to the investigation, the information must be forwarded to Medtronic. The investigator shall prepare and submit in a complete, accurate and timely manner the reports listed in Table 5.

Table 5: Investigator Reports

Report	Submit To	Description / Constraints
Withdrawal of EC approval	Medtronic	report required by local law
Study Deviations	Medtronic, EC or competent authorities or other regulatory bodies	Any deviation from the CIP shall be recorded together with an explanation for the deviation. Deviations shall be reported to the sponsor who is responsible for analyzing them and assessing their significance. Note: When relevant, Ethics Boards, competent authorities or the appropriate regulatory bodies should be informed.
Failure to obtain informed consent	Medtronic, EC	Notification within five working days.
Progress Reports (if required)	Medtronic, EC	Provide if required by local law or Ethics Board

1.3.3 Sponsor records

At a minimum, the sponsor will keep the following records:

- All essential study documents and correspondence that pertains to the clinical study
- CIP and, if applicable, any amendments
- Investigator Brochure and Instructions for Use
- Sample of labeling attached to the investigational device
- Curriculum vitae of investigators and site staff
- Delegated Task Lists and training records of investigators and site staff
- Study training records of Medtronic personnel involved in the study
- EC approvals/notifications and regulatory approvals/notifications
- Signed Clinical Investigation Agreements and signed agreements with third parties
- Insurance certificates,
- Medtronic and EC approved Patient Informed Consents/Data Release Forms
- Monitoring visit reports
- Adverse event and Device Deficiency reports
- Financial disclosure information, if local requirements
- Fully executed eCRFs and corrections
- Connection box traceability record containing serial numbers of connection boxes, shipping date and name and address of person that received shipped connection box, location (if different than person shipped to), transfer and receipt by Medtronic dates
- Names of the institutions in which the clinical investigation will be conducted
- Correspondence with authorities as required by national legislation

- Final report of the clinical investigation
- Any other records that local regulatory agencies require to be maintained

